8.0 DETAILS OF RISK

8.1 Risks from radiotracers

lonising radiation dose to the patients coming from the injection of radiotracers or exposure to external radiation source (CT or Transmission scans) will be kept following ALARA ("As Low as Reasonably Achievable" principle). [¹⁸F]GE-180 is a developmental unregistered Investigational Medicinal Product whose safety profile is still under investigation; therefore undocumented side effects may occur. The effective dose for the full research study to each patient is around 9 mSv, which is for Phase I study which includes both radiotracer injections (C-11) Pk11195 and (F-18) GE-180. For Phase II study, there will be only one radiotracer injection (F-18) GE-180, and the effective dose corresponding is 5.5 mSv. These effective doses have been calculated using target injection activities. The equivalent radiation background received in UK per year is 2.7 mSv; therefore the equivalent UK background equivalent is 3.3 years for full study or Phase I

and 2 years for Phase II. In both cases the patient will received less than 4 times the normal dose of radiation that individuals are normally exposed to when living for one year in the United Kingdom in a normal environment.

For a healthy adult of 30-40 year old the estimated lifetime risk of fatal cancer associated with the total Phase I part of the study (9 mSv) is 1 in 2000 and as for Phase II the risk is 1 in 3400 (using UK specific detriment of 5.3*10-5 per mSv NRPB R260).

Study team must remain vigilant for at least 1 hour after the injection of GE-180 to observe subjects for signs of possible anaphylactoid reactions and other emergencies after dosing and access to appropriate clinical supplies must be immediately available

8.2 Risks from scans

Exposure to magnetic resonance scans poses a very small risk related to possible interaction of metal bodies with the strong magnetic field. These will be minimised by following the standard operating procedures applied to all studies held at WMIC that involve a MRI and/or PET scans.

9.0 TRIAL ASSESSMENTS

PHASE 1

Table 1. Schedule of assessment for phases 1 and 2.

		Trial Procedure (ARM A)		Trial Procedure (ARM B)		3 months after stroke**
	Screening Assessment*	Visit 1	Visit 2	Visit 1	Visit 2	
		Assessm	ents			
National Institutes of Health Stroke Scale (NIHSS)	Х					X
Modified Rankin Scale (mRS)	Х					х
Tolerability questionnaire			Х	Х		
Adverse Event Log		Х	Х	Х	Х	Х
Concomitant/Prohibited Medications	Х	x	Х	Х	х	
		Tests	5			
Blood tests***		х		х		
MRI scan (with and without contrast) ⁺		X+	X+	X+	X+	
PET scan ([¹¹ C]-(R)- PK11195)		X			х	
PET scan ([¹⁸ F]GE- 180) ****			х	Х		

* Carried out whilst patient is still in hospital ** Carried out at the hospital site *** Whole blood sample (3ml EDTA tube) and plasma sample (2ml cryovial) **** Two blood samples of 10ml each may be taken per scan for the measurement of radioactivity.

⁺ To be carried out on either Day 1 or Day 2.

PHASE 2

	Screening Assessment*	Trial Procedure	3 months after stroke**		
	Assessi	ments			
National Institutes of Health Stroke Scale (NIHSS)	Х		Х		
Modified Rankin Scale (mRS)	Х		Х		
Adverse Event Log		Х	Х		
Concomitant/Prohibited Medications	Х	Х			
Tests					
Blood tests***		Х			
MRI scan (with and without contrast)		х			
PET scan ([¹⁸ F]GE- 180)****		Х			

* Carried out whilst patient is still in hospital

** Carried out at the hospital site

*** Whole blood sample (3ml EDTA tube) and plasma sample (2ml cryovial)

**** Two blood samples of 10ml each may be taken per scan for the measurement of radioactivity.

Two weeks after initial stroke, most patients would expect to switch tablets from aspirin to clopidogrel as a national recommendation. At each scan visit, a vein will be cannulated for the scanning procedure. Venous access is needed for the administration of the contrast agent in Magnetic Resonance Imaging (MRI) and of the radiopharmaceutical in Positron Emission Tomography (PET). The cannula can be removed on completion of the visit that day. If possible, blood will be taken from the administration cannula at the time of insertion. This can be sometimes difficult and may necessitate a further venepuncture for another blood sampling cannula.

Three types of blood analysis may be performed.

- The concentration of peripheral inflammatory markers such as C-Reactive Protein (CRP) and Interleukin 6 (IL6) in plasma will be measured. This is to study the relationship between markers of peripheral inflammation and markers of inflammation in the central nervous system.
- Genomic DNA will be extracted from whole blood (3ml EDTA tube). The affinity of the binding to [¹⁸F]GE-180 will be classified as high affinity binder (HAB), medium affinity binder (MAB) or low affinity binder (LAB) by analysing the rs6971 genotype of the participant (Owen et al., 2012).
- 3. Measurements of [¹⁸F]GE-180 activity in the venous plasma samples taken before and after the PET emission scan will be performed. These are used to assess whether the transient equilibrium analysis (Carson et al., 1993) is a valid approach and to optimise the time window past injection when the [¹⁸F]GE-180 emission scan is acquired.

During the study period, the treating clinician may have organised additional tests such as heart tests or other blood tests. Patients should be strongly encouraged to keep these appointments. It is routine for a patient to be offered a follow up appointment in the stroke clinic at approximately 6-8 weeks after their stroke. If the patient is an inpatient then we will liaise with the medical and therapy services in order to minimise any impact of travel to WMIC on the clinical care.

Three months (\pm 2 weeks) after the initial stroke patients will return to the hospital site for follow up. Patients will be assessed by the clinical team to assess if they have had any other symptoms that would indicate a recurrent stroke. The NIHSS and mRS will be assessed for second time as outcome measures.

10.0 TRIAL CLOSURE

All patients will be followed up 3 months (± 2 weeks) after their initial stroke.

The first possible endpoint is at the end of year 1. If the trial does not satisfy the 'Go/NoGo' criteria (defined in section 4) the trial will be closed. All patient data gathered in the first year will be kept by WMIC and used for analysis.

The data acquisition endpoint is at the end of 39 months. Data will have been collected on 50 patients (excluding any low -binding patients as described in previous sections).

The final endpoint of the trial is at the end of 4 years (39 months of data collection plus 9 months of scanning analysis and statistical analysis of the correlation between microglial activation and the functional outcome of the patients). All data collected from phases 1 and 2 will have been analysed.

11.0 STATISTICS AND DATA ANALYSIS

11.1 Sample size calculation

The project is primarily a feasibility study aimed at obtaining provisional evidence that baseline PET scan data are useful predictors of clinical outcomes. In the context of clinical trial development, it is recommended that not too much emphasis should be placed on formal power calculations for the evaluation of statistical significance at this stage [Lancaster *et al.* (2004)], but that investigators should concentrate, instead, on confidence interval estimation. The main analytical question to be answered by the present project is whether baseline PET score measurements can predict (i.e. are associated or correlated with) clinical outcome in stroke survivors. We assume that to be of any utility the correlation would have to be at least 0.40 (explaining about 16% of the variation in outcome). Taking this to be the true value and assuming bivariate normality, we obtain the following result: when the sample size is 37, a one-sided 90.0% confidence interval for rho=0.400 will have limit 0.200 (*nQuery Advisor*). It is expected that the analysis will be based on at least 40 participants with non-missing data. The allowance for loss to follow-up using probability weights should have little impact on the precision of the estimates (but probably making them marginally less precise), but the inclusion in the prediction model of baseline covariates with known prognostic value should lead to increased precision.

11.2 Interim analysis

The interim analysis will be carried out at the end of phase 1. It will be based on the feasibility of obtaining scans on patients who heterozygous for the TSPO rs6971 polymorphism. The analysis will also include information from the tolerability questionnaires that patients will be asked to complete at the end of the 2 day scanning process.

Main objective is to obtain information on:

- Technical feasibility of the [¹⁸F]GE-180 scans and the possibility of reducing the scan time to 20 minutes.
- Use tolerability information gathered from patients about the comfort and duration of the scans.
- Ensure that the correlation between [¹¹C]-(R)-PK11195 and [¹⁸F]GE-180 images has a coefficient correlation of 0.5 or higher.

11.3 Image analysis

The MR images will be used to assess the integrity of the blood-brain barrier and to provide anatomical information for a region-of-interest analysis of the PET images.

Dynamic PET data from the [¹¹C]-(R)-PK11195 scans will be processed as previously described (Su et al., 2013). Principally, characterisation of the radiotracer binding in the lesion target areas (infarct core and periphery, affected white matter tracts) will be based on the comparison with an appropriate reference region(s) in the contralateral hemisphere. Thus, each study participant serves as its own control avoiding the scanning of a separate control cohort in this clinical trial.

Summed PET images will be calculated from the [¹⁸F]GE-180 data, and for comparison by correlation analysis also of [¹¹C]-(R)-PK11195, enabling visual assessment and semi-quantitative analyses based on target-to-reference region ratios. Of particular interest is the quality of the [¹⁸F]GE-180 static images governed by the length of the image acquisition and the injected activity, two adaptable scanning parameters.

11.4 Primary and secondary analysis

Factors associated with three-month mortality

Although death of the participant precludes measurement and analysis of other clinical outcomes such as the NHSS and mRS this is not a missing data problem in the conventional sense: it is itself a particularly important outcome. We expect the three-month mortality to be less than 10%. The initial analysis will explore the relationship between baseline characteristics (including the imaging biomarker measurements). This analysis will be primarily descriptive and informal – there will be insufficient data to enable the development of a robust risk prediction model. Subsequent analyses (described below) will be carried out to infer patterns of clinical outcome in those who have not died. That is, the target population will be the stroke survivors.

Factors associated with loss to follow-up (other than death) – construction of inverse probability weights

In total, it is anticipated that about 10-15% of the surviving stroke patients will have missing clinical outcome data. As long as the attrition is kept lower than 15%, it would be expected to have only a small effect on statistical precision and, similarly, only a small impact on bias in the estimates of the regression coefficients in the prediction models (see below). However, associations between baseline characteristics and loss to follow-up will be examined both descriptively and through the use of logistic regression modelling. Predicted probabilities of follow-up will be used to compute inverse probability weights to ensure that the observed outcomes fairly represent the full cohort of stroke survivors [Dunn G (2000)]. There are likely to be three sources of missing data: (a) initial diagnosis not validated at the time of follow-up - presumably, there will be very few of these; (b) discontinuation and drop-out; and (c) machine failure (although there will be opportunities for a second appointment to rectify this problem). Group (b) will be the main focus of the analyses, although the possibility of (a) and (c) not occurring completely at random will be investigated.

Development and validation of clinical prediction models

All analyses of clinical outcomes in the stroke survivors will be carried out using the *regress* command of *Stata*, incorporating inverse probability weights to allow for attrition using Stata's *pweight* option. The statistical significance of any predictive effects will be evaluated using robust standard errors, p-values and associated confidence intervals (using the Huber-White 'sandwich' estimator). Prediction models include the relevant PET scan variable, TSPO Ala147Thr polymorphisms (high versus medium) and the possibility of an interaction between the two. Other baseline demographic and clinical covariates will be added to the model so that the 'unique' contribution of the PET scan data can be assessed (i.e. how much information does it provide over and above the routinely collected demographic and clinical variables?). We will be giving considerable attention to confidence interval estimation rather just relying on statistical significance.

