2.2 Phase 2 Objective

The objective for phase 2 of the study is to determine whether the extent of neuroinflammation has an impact on the severity and prognosis of clinical impairment.

To assess whether imaging of microglial activation predicts outcome and clinical progression in patients with stroke, the clinical status will be compared to the degree of neuroinflammation. The clinical status will be determined using:

A) The Modified Rankin Scale (mRS), which is being used in most stroke trials as a clinical indicator of the severity of impairment will be assessed.

B) The National Institutes of Health Stroke Scale (NIHSS), which provides a finer grained indicator of functional and neurological impairment will be assessed.

The neuro-inflammation will be assessed using:

A) A comparison between [¹⁸F]GE-180 PET findings with the extent of changes in proton diffusion and late structural damage by MRI will be determined.

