3.0 TRIAL DESIGN

3.1 Overall design

This study aims to recruit 50 patients in total receiving standard of care stroke assessments. Patients in phase 1 (n=10) will be asked to have two PET scans (using $[^{11}C]$ -(R)-PK11195 and

[figure not shown]
[¹⁸F]GE-180) and two MRI scans (one with and one without contrast). If the phase 1 analysis is favourable, the project will progress to phase 2. Patients in the second phase will be asked to have one PET scan (using [¹⁸F]GE-180) and two MRI scans (one with and one without contrast). All patients will remain on the study for 3 months after the onset of the stroke , at which point they will have outcome assessments (mRS and NIHSS). Following this, their participation in the study will cease and no further follow-up data will be captured. Patients will receive supportive care as per standard practice.

The study aims to recruit 10 patients in the first year, estimating a rate of 1 per month per NHS site, enabling 2 months for phase 1 review. Phase 2 estimated accrual for this study estimated at 2 patients per month. Thus, patient accrual is expected to be completed within 24 months. The total duration for phase 1 recruitment and analysis (12 months) analysis and phase 2 (24 months recruitment + 3 months for follow-up) recruitment is 39 months. The following 9 months will be dedicated to analysing the scans and completing coefficient correlation analysis on the outcome measure and the neuroinflammation. The total duration of the study is 48 months.

The study is designed to determine whether ¹⁸F-GE-180 PET as a biomarker can predict the clinical outcome in patients with cerebrovascular disease (CVD). Patients with sub-acute stroke of mild to moderate severity will be studied using standard research techniques and following the Quality Assessment of Diagnostic Accuracy Studies (QUADAS) criteria for diagnostic studies. In particular, the study protocol will ensure:

- patient selection based on standard diagnostic criteria
- short time interval between initial clinical assessment and PET
- verification of diagnosis at the time of follow-up
- independence of clinical diagnosis and clinical assessment from the result of the index test (PET) by blinding of clinical staff to PET results
- inclusion of failed and uninterpretable test results or withdrawal of consented patients into the final report

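### Death is said to rule out an mRS analysis, so this secondary outcome is modelled in survivors only, although death can be ranked as the worst category

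*Protocol*

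**What the plan says.** Section 3.3 makes 3-month NIHSS, with baseline as a covariate, the primary outcome. The mRS and its change are secondary. Section 4.1 limits entry to mRS 1 to 3.

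The mortality part of section 11.4 begins with the clause "Although death of the participant precludes measurement and analysis of other clinical outcomes such as the NHSS and mRS". It adds that death is not missing data in the usual sense but an important outcome, and expects 3-month mortality below 10%. Death is to be explored first, against baseline characteristics that include the imaging biomarker. That analysis is descriptive because the data will not support a robust risk model. For everything that follows, "the target population will be the stroke survivors".

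The modelling part fixes the method: "All analyses of clinical outcomes in the stroke survivors will be carried out using the" regress command of Stata, that is, linear regression, with inverse probability weights and sandwich standard errors. The weights address loss to follow-up other than death and are meant to represent the full cohort of survivors.

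Section 11.1 also words the main analytical question for survivors. Section 2.2 is wider: it asks whether microglial imaging "predicts outcome and clinical progression in patients with stroke". Section 2.0 likewise speaks of severity and prognosis in stroke patients.

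**The concern.** The protocol states as fact that a patient who dies cannot contribute to the mRS analysis. That is a choice, not a necessity. An ordered scale needs only a ranking, and death can be ranked worse than any disability grade. The protocol does not list the mRS grades, and the argument does not depend on them.

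Survival is settled after the PET scan, and the PET signal may itself predict it. If it does, restricting the model to survivors removes patients from the worst end of the outcome and weakens the association under study. The weights cannot repair this, because they rebuild the survivor cohort and not the whole one. The few deaths are too sparse for a model of their own, as the protocol says, but they would carry information if ranked within the mRS.

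**Working it through.** **1. The plan's own figure.** Section 11.1 starts from "We assume that to be of any utility the correlation would have to be at least 0.40" and states: "when the sample size is 37, a one-sided 90.0% confidence interval for rho=0.400 will have limit 0.200". With Fisher's z:

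n = [z(0.90) / (atanh 0.40 − atanh 0.20)]² + 3 = [1.2816 / (0.4236 − 0.2027)]² + 3 = 36.65, rounded up to 37.

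The figure reproduces. The lower limit is 0.201 at n = 37 and 0.210 at n = 40.

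**2. Number of deaths and patients analysed.** Section 3.1 gives the sample: "This study aims to recruit 50 patients in total receiving standard of care stroke assessments". Mortality below 10% of 50 means fewer than 5, so at most 4 deaths. Section 11.4 expects 10 to 15% of survivors to lack outcome data.

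| | Survivors analysed | With deaths kept |
|---|---|---|
| 4 deaths, 10% loss | 46 × 0.90 = 41.4 | 45.4 |
| 4 deaths, 15% loss | 46 × 0.85 = 39.1 | 43.1 |
| 10% ceiling, 10% loss | 45 × 0.90 = 40.5 | 45.5 |
| 10% ceiling, 15% loss | 45 × 0.85 = 38.25 | 43.25 |

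Section 11.1 says: "It is expected that the analysis will be based on at least 40 participants with non-missing data". At 15% loss the survivor count falls slightly short of 40 but stays above 37.

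**3. Attenuation from dropping deaths.** Assume that PET signal and outcome are bivariate normal with correlation 0.40 in all patients. Death removes the top fraction d of a latent score whose correlation with outcome is a. Put c = z(1 − d), λ = φ(c)/(1 − d) and k = λ(λ + c). Among survivors:

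r = 0.40(1 − a²k) / √[(1 − a²k)(1 − 0.16a²k)]

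At d = 10%: c = 1.2816, λ = 0.195, k = 0.288.

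- Extreme case, a = 1 (the deaths are exactly the worst outcomes): 0.2848 / √(0.7121 × 0.9539) = 0.346.
- Partial dependence, a = 0.7 (assumed): 0.3436 / √(0.8589 × 0.9774) = 0.375.

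| Mortality | Partial (a = 0.7) | Extreme (a = 1) |
|---|---|---|
| 5% | 0.384 | 0.365 |
| 8% (4 of 50) | 0.378 | 0.353 |
| 10% | 0.375 | 0.346 |

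A simulation of 4 million pairs gives the same values at 5% and 10%. At n = 40 the one-sided 90% lower limit falls from 0.210 to between 0.18 and 0.19 under partial dependence, and to 0.149 in the extreme case at 10%.

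**4. What keeping deaths recovers.** In the extreme case, with deaths held as one tied worst rank, the Spearman correlation stays at 0.384 at 5% mortality and 0.383 at 10%. In survivors only it is 0.352 and 0.332.

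**5. Deaths or model?** The two changes can be separated by simulation: 46 patients, 7.5% deaths, 600 trials per setting, with assumed mRS cut-points and baseline effect. Death is generated as the top grade of the same PET-driven scale. Power was:

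| PET log-odds per SD | Linear, survivors | Ordinal, survivors | Linear, all | Ordinal, all |
|---|---|---|---|---|
| 0.7 | 59% | 62% | 68% | 71% |
| 1.0 | 81% | 84% | 91% | 93% |

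Keeping deaths adds 9 to 10 points. The ordinal model adds 2 to 3. With no true effect, the ordinal test rejected in 7.5 to 8.0% of trials and the linear test in 6.2 to 7.3%, so part of that small gain may be inflated size.

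**The case against.** The strongest reply is that the protocol chose its population on purpose. Sections 11.1 and 11.4 both name survivors, so attenuation is a bias only against an all-patients question that section 11 does not pose. The planning value of 0.40 is itself set for survivors. This stands. It rules out calling the plan contradictory, and the gap to sections 2.0 and 2.2 is one of scope.

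Several stronger readings are tempting, and the documents do not support them:

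- *Deaths are thrown away.* They are not. Death is examined first, against the imaging marker, with a fair reason for staying descriptive.
- *The primary analysis is invalid.* The primary outcome is NIHSS, for which no grade for death is documented. A survivor analysis of it is a legitimate declared target.
- *The weights mishandle deaths.* They are already confined to non-fatal loss.
- *The sample size is wrong.* The 37 reproduces, and the lower limits above rest on assumptions that the protocol does not make.
- *Linear regression of the mRS is a serious fault.* Sandwich errors do not remove the equal-spacing assumption, but step 5 shows little practical cost, and this is a secondary outcome in what the protocol calls primarily a feasibility study.

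The effect is also small beside sampling error. The standard error of a correlation of 0.40 at n = 40 is about (1 − 0.16)/√39 = 0.13, against a shift of 0.016 to 0.025 under partial dependence.

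The reply does not rescue the stated reason. The claim that death prevents analysis of the mRS remains incorrect, and the protocol itself fixes both the population and the model.

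**Conclusion.** The point holds in a limited form. The sentence in section 11.4 is wrong for the mRS, and it is the reason given for leaving deaths out of the secondary outcome model. The resulting analysis answers a narrower question than sections 2.0 and 2.2 ask.

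The size depends on mortality (stated only as below 10%) and on how closely death follows the PET-related outcome (not stated, so assumed). Taking 0.40 as the correlation in all patients, the loss is 0.016 to 0.025 at 5 to 10% mortality under partial dependence, and 0.054 at the 10% ceiling if deaths are exactly the worst outcomes. If death is unrelated to the PET signal and to outcome, there is no attenuation, only the loss of up to 4 patients. The power figures also assume that death lies on the same PET-driven scale, so they illustrate direction and do not forecast this trial.

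**What to change.** 1. Reword the sentence in section 11.4: death prevents measurement of the NIHSS, but can be ranked as the worst category of the mRS.
2. Analyse 3-month mRS in all patients with known vital status, with death as the worst category, by ordinal or rank-based regression adjusted for baseline mRS and the planned covariates. Survivors carry their planned weights and deaths a weight of 1. Change in mRS, which has no natural value after death, can stay a survivor summary.
3. Keep NIHSS in survivors as the primary analysis. Add one sensitivity analysis that ranks deaths worse than any observed NIHSS.
4. Leave the construction of the inverse probability weights as it is.

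The cost is wording, one changed secondary model and one sensitivity analysis. The 3-month mRS is already scheduled (section 9), and deaths are recorded on the CRF or the SAE form (section 12.1). The downside is that the mRS effect becomes an odds ratio or rank effect that mixes death with disability, so the survivor result and the death count should be reported beside it. The gain comes mainly from keeping the deaths. The ordinal model adds little by itself.

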3.3 Outcome measures

The primary outcome measure will be the functional score on the NIHSS at clinical follow-up after 3 months. The baseline value will be taken into account as a covariate. The Modified Rankin Scale and its change during follow-up will be analysed as a secondary outcome parameter.

 Imaging and outcome parameters will also be correlated with CRP as a marker of systemic inflammation. Regional image analysis will be performed to relate cognitive and motor symptoms with the brain location of structural abnormalities on MR and microglial activation on PET. Technical feasibility of the [¹⁸F]GE-180 scans and the possibility of reducing the scan time to 20 minutes are also among the outcome measures.

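### With about 40 patients, the sandwich standard errors fixed in section 11.4 give intervals that are somewhat too narrow; section 11.1 should also say that its 0.200 limit is for an unadjusted correlation

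*Protocol*

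**What the plan says.** Section 11.4 puts all clinical-outcome analyses in survivors into Stata's regress command with inverse probability weights for attrition. Predictive effects are to be "evaluated using robust standard errors, p-values and associated confidence intervals", with the Huber-White sandwich named as the estimator and no small-sample variant mentioned. The model holds the PET variable, genotype (high versus medium binder), possibly their interaction, and an unstated number of further baseline covariates. The aim is to isolate what PET adds to routine variables. For the primary outcome, NIHSS at three months, section 3.3 adds: "The baseline value will be taken into account as a covariate".

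Section 11.1 sets formal power aside in favour of interval estimation. It requires that "the correlation would have to be at least 0.40 (explaining about 16% of the variation in outcome"), and continues: "Taking this to be the true value and assuming bivariate normality", the result is that "when the sample size is 37, a one-sided 90.0% confidence interval for rho=0.400 will have limit 0.200". It expects that "the analysis will be based on at least 40 participants with non-missing data". It also says that the weights should matter little for precision and that "the inclusion in the prediction model of baseline covariates with known prognostic value should lead to increased precision".

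**The concern.** The Huber-White sandwich is justified in large samples. With about 40 patients, several coefficients and unequal weights, high-leverage patients pull the fit towards themselves. Their residuals are then too small, and so is the variance built from them. The protocol makes intervals its main product, so an interval method that runs short bears directly on what will be reported.

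The second issue is one of description. The only precision figure in the protocol is for a two-variable correlation without covariates or weights. The quantity to be reported is an adjusted PET effect. A reader could take the lower limit of 0.200 as what the final model will deliver, although the adjusted correlation may be larger or smaller than the raw one.

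**Working it through.** **1. The plan's own figure.** Inputs from section 11.1: rho 0.40, limit 0.20, one-sided 90% (z = 1.2816).

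n = (1.2816 / (atanh 0.40 − atanh 0.20))² + 3 = (1.2816 / (0.4236 − 0.2027))² + 3 = 36.65, so 37. The limit is 0.201 at n = 37 and 0.210 at n = 40. The figure reproduces as a simple correlation.

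**2. Patients analysed.** From 50 patients, with 0-10% deaths and 10-15% of survivors missing (section 11.4): 50 × 0.90 × 0.85 = 38 to 50 × 1.00 × 0.90 = 45. This agrees with the stated minimum of 40.

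**3. Coefficients.** Intercept, PET, genotype and baseline NIHSS make 4. The interaction makes 5 and one further covariate 6. The protocol gives no total.

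**4. Sandwich at this size.** The variance is (X'WX)⁻¹ X'W diag(e²) WX (X'WX)⁻¹ × n/(n−k), with a t(n−k) reference, taken here to be the software default. HC3 uses e/(1−h) for each residual and drops the scaling factor.

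Assumptions not in the documents:
- 46 survivors, about 40 analysed, with dropout depending on baseline severity and weights estimated by logistic regression.
- 40% heterozygotes and a centred interaction.
- PET normal or moderately right-skewed; outcome normal or NIHSS-like counts.
- A true PET effect of zero.

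There were 8,000 runs per row, so the Monte Carlo error at 7.5% is √(0.075 × 0.925 / 8000) = 0.3 percentage points.

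| Coefficients | PET | Outcome | Sandwich, 5% two-sided | HC3, 5% two-sided | Sandwich, one-sided 10% | Mean SE / true SD |
|---|---|---|---|---|---|---|
| 5 | normal | normal | 7.2% | 4.1% | 11.3% | 0.93 |
| 5 | normal | NIHSS-like | 7.4% | 3.7% | 12.3% | 0.91 |
| 5 | skewed | normal | 8.4% | 3.8% | 12.5% | 0.89 |
| 5 | skewed | NIHSS-like | 8.6% | 3.5% | 12.6% | 0.87 |
| 8 | normal | normal | 7.3% | 3.0% | 11.5% | 0.92 |
| 8 | normal | NIHSS-like | 7.0% | 2.8% | 11.8% | 0.91 |
| 8 | skewed | normal | 8.1% | 3.0% | 12.5% | 0.90 |
| 8 | skewed | NIHSS-like | 8.7% | 2.9% | 12.7% | 0.87 |

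Repeats with 4 to 6 coefficients, with and without the interaction, gave 6.5-8.9% for the two-sided test and standard errors 5-13% too small. Other runs of the same kind reached about 9.5%. In harsher cases (n = 40, known weights), strongly skewed PET gave 10-12%. Error variance rising with PET gave 9.6% with normal PET, 15% with moderately skewed PET and about 24% with strongly skewed PET.

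**5. What the 0.200 limit becomes after adjustment.** If the partial correlation itself is 0.40 and three terms are adjusted for, the limit at n = 40 is tanh(0.4236 − 1.2816/√(40−3−3)) = 0.201. Lost degrees of freedom therefore cost almost nothing.

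If 0.40 is instead the raw correlation, let c be the PET-baseline NIHSS correlation and 0.6 the baseline-outcome correlation (both assumed). Then:
- partial = (0.40 − 0.6c) / √((1−c²)(1−0.36))
- limit = tanh(atanh(partial) − 1.2816/√34)
- R² = (0.16 + 0.36 − 2 × 0.40 × 0.6c) / (1−c²)
- SE ratio, adjusted to unadjusted = √[ ((1−R²)/(1−c²)) / (1−0.16) ]

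| c | Partial | Limit, n = 40 | SE ratio for PET |
|---|---|---|---|
| 0 | 0.50 | 0.32 | 0.76 |
| 0.1 | 0.43 | 0.23 | 0.79 |
| 0.2 | 0.36 | 0.15 | 0.83 |
| 0.3 | 0.29 | 0.08 | 0.88 |
| 0.4 | 0.22 | 0.00 | 0.93 |

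At c = 0.3, R² = 0.413, (1 − 0.413)/0.91 = 0.645, and √(0.645/0.84) = 0.88. The SE falls by 12% while the limit falls to 0.08. The gain in SE disappears only near c = 0.5.

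**The case against.** The protocol calls the project primarily a feasibility study and states no 5% two-sided test. The only confidence level it gives is one-sided 90%, where the error is 11-13% instead of 10%. This stands, and it makes the defect moderate. It does not remove it, because section 11.4 applies the sandwich to every p-value and interval.

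A statistical analysis plan, not shown here, could name a small-sample variant. That is fair in general, but the protocol does not leave the estimator open. It names the uncorrected one for an expected 40 or so patients.

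A reader might infer three stronger criticisms that the documents do not support:
- That n = 37 is wrong. It reproduces, and a partial correlation of 0.40 with three extra terms still has a limit of 0.201 at n = 40.
- That the remark about covariates and precision is wrong. In every scenario tabulated the SE of the PET coefficient falls after adjustment. The lower limits at higher c come from a smaller adjusted correlation, not from lost precision.
- That the PET coefficient will describe one genotype group only. Section 11.4 mentions only the possibility of an interaction and fixes neither the coding nor the contrast to be reported.

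**Conclusion.** The point holds at moderate size. At about 40 patients the named estimator gives standard errors roughly 4-15% too small. It gives about 6.5-9.5% rejection at a nominal 5% and about 11-13% error for a one-sided 90% bound. The sizes depend on the assumed PET distribution, heterozygote share, covariate count and error variance. The direction was the same in every setting tried, and strong skewness or unequal variance makes it worse.

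On section 11.1, only a clarification is needed. The 0.200 limit is correct for a raw correlation. It does not describe the adjusted effect that section 11.4 targets, whose limit could lie above or below it: 0.32 to 0.08 for c from 0 to 0.3, given a raw 0.40 and an assumed baseline-outcome correlation of 0.6.

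**What to change.** In section 11.4, replace the default sandwich with a small-sample version for all intervals and p-values. Either use a patient-level jackknife or bootstrap that re-estimates the inverse probability weights in each replicate, or use HC3 if regress accepts it with probability weights, which must be checked first. With only about six patients lost, the weight model may fail in some replicates, so the text should say how such replicates are handled. The resampling options were not simulated here.

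In section 11.1, state that n = 37 and the limit of 0.200 refer to an unadjusted correlation. Add the limit for the partial correlation over a range of PET-baseline NIHSS correlations, as in the second table. Keep the sentence on covariates and precision.

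The cost is a changed sentence in 11.4, some analysis code and a few lines in 11.1, with no change to patients, visits or sample size. The statistical price is wider intervals: HC3 standard errors were about 15-40% larger than the default sandwich (12% in the mildest run). They were slightly conservative, rejecting roughly 3-5% at a nominal 5%.
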